## 5.3. Lifestyle Considerations

# 5.3.1. Meals and Dietary Restrictions

No dietary restrictions are required before or after dose administration.

#### 5.3.2. Caffeine, Alcohol, and Tobacco

Participants must abstain from ingesting caffeine- or xanthine-containing products (e.g., coffee, tea, cola drinks, and chocolate) for 48 hours prior and during quarantine and for 48 hours prior to all visits requiring spirometry.

Participants must not consume alcohol for 72 hours prior and during quarantine and for 72 hours prior to any clinic visits.

Participants must not smoke, use tobacco or any nicotine containing products for 72 hours prior to and during quarantine Participants that are current smokers may be continued in the study if, in the opinion of the PI, cessation of smoking during quarantine will not lead to withdrawal symptoms which could interfere with the accurate recording on the Symptoms Diary Card.

# 5.3.3. Activity

Participants will abstain from strenuous exercise for 48 hours prior and during quarantine and for 48 hours prior to each clinic visit (unless it is within the usual activity of the participant).

#### 5.4. Screen Failure

Screen failures are defined as participants who sign the study specific Informed Consent Form (ICF) but are not subsequently randomised to receive the study Intervention.

For individuals who do not meet the criteria for participation in this study (screen failure), the Investigator will decide whether the participant should be permanently excluded from the study or invited back for repeat assessments (i.e. repeat clinical laboratory test) if the initial screening assessments are still within the allowed screening windows (-28 to -1 days for Part 1 and -56 to -4 days for Part 2) or rescreening for a later quarantine, as appropriate.

# 6. Study Intervention

Study interventions administered to participants are described in Table 2.

# 6.1. Study Intervention(s) Administered

**Table 2 - Study Interventions** 

Intervention Name	Palivizumab	Placebo	RSV-A Memphis 37b virus	
Туре	Biologic	Other	Virus	
Dose Formulation	Liquid solution (50mg or 100mg) in sterile water for injection to give a final concentration of 20mg/mL	Sodium Chloride 0.9% Solution (Normal Saline)	Cryovial, Liquid	
Unit Dose Strength(s)	
 
8 mg/kg for Part 1
 
8 mg/kg or 15 mg/kg for Part 2
 
	Not applicable	The inoculum virus titre is determined in an infectivity (plaque) assay, the titre is reported in plaque forming units per mL (PFU/mL). The challenge dose is approximately 4.5log 10 PFU.	
Dosage Level(s)	
 
A single dose of 8mg/Kg, or
 
A single dose of 15mg/Kg
 
	A single dose of 0mg/Kg	A single dose of virus will be delivered.  Dose volume delivery method is provided in the Analytical Plan	
Route of Administration	Infusion IV	Infusion IV	Intranasal	
Use	Reference article	Placebo control	nfectious Challenge agent	
IMP and NIMP	IMP	IMP (Placebo) NIMP Challenge virus		
Sourcing	Sponsor	Provided centrally by hVIVO	Provided centrally by hVIVO	
Packaging and Labelling	Study intervention will be provided as	Study intervention will be provided as	RSV Challenge Inoculum will be provided in vials. The	

hVIVO template identifier: (G\_0687) v3.0

	individual doses in single use sterile Latex/DEHP Free syringes, prepared, labelled and QP released by Hammersmith Medicines Research (HMR) Pharmacy (London) holding MIA (IMP) licence.	individual doses in single use sterile Latex/DEHP Free syringes, prepared, labelled and QP released by Hammersmith Medicines Research (HMR) Pharmacy (London) holding MIA (IMP) licence.	details of the virus challenge agent packaging and labelling will be provided in the Analytical Plan
Current/Former Name(s) or Alias(es)	Synagis ™	n/a	n/a

All supplies indicated in Table 2 will be provided per the "Sourcing" row depending upon local country operational requirements. If local sourcing, every attempt should be made to source these supplies from a single lot/batch number where possible (e.g. not applicable in the case where multiple lots or batches may be required due to the length of the study).

Refer to Section 6.2 and the pharmacy manual for details regarding administration of the study intervention.

## 6.2. Preparation/Handling/Storage/Accountability

#### 6.2.1. Dose Preparation

Storage and manufacture of the Investigational product will be based on SmPC. Palivizumab and placebo will be prepared by an unblinded pharmacist for each individual participant. Dose preparation procedures will be described in the pharmacy manual and as described in Hicks *et al.* (Hicks, Chemaly, and Kontoyiannis 2003).

# 6.2.2. Handling, Storage, and Accountability

#### Interventional Product / Placebo:

Bulk supplied of the Investigational product will be stored at HMR Pharmacy. Individual ready-to-dispense Interventional product / Placebo doses will be prepared by unblinded pharmacist, Qualified Person (QP) released and delivered to hVIVO prior to administration of the treatment to the participant.

HMR Pharmacy and hVIVO will maintain drug accountability as detailed in the Pharmacy Manual.

The Investigator will ensure that all supplies are received by a responsible person, all deliveries and returns are documented and signed for, and the condition of the Interventional product / Placebo is monitored. Accurate records will be kept of when and how much Interventional product / Placebo is dispensed and used in the study. Any reasons for departure from the protocol dispensing regimen must be recorded.

Accountability records will be available for verification by the Study Monitor at each monitoring visit. At the completion of the study, there will be a final reconciliation of all Interventional product / Placebo.

#### **Challenge Virus**

The RSV-A Memphis 37b challenge virus was produced via a nasal aspirate collected from a paediatric patient infected with RSV. The Challenge Virus stock, RSV-A Memphis 37b, was manufactured under current good manufacturing practices (cGMP). The Challenge Virus stock has undergone quality testing performed during manufacturing (identity, appearance, sterility, infectivity, and contaminants) according to pre-determined specifications, and has subsequently also passed an extensive panel of adventitious agent testing. The Challenge virus is stored in a secure -80°C freezer (normal temperature range -60°C to -90°C).

Challenge Virus inoculum will be prepared according to the hVIVO Analytical Plan (AP) and administered in accordance with hVIVO's standard operating procedures (SOPs). Each participant will be allocated a unique vial containing the Challenge Virus and will receive the inoculum intranasally.

The time from the Challenge Virus inoculum thawing to inoculation should be no longer than 2 hours. All administrations will be made by a member of the clinical team and witnessed by a second member of the team. The exact time of inoculation will be recorded in the administration log. Accurate records will be kept of when and how much study inoculum is prepared and used. The oversight process will be signed off prior to administration of the Challenge Virus. Any non-compliance or problems with the inoculation will be recorded in the participant's source notes and reported to the PI.

Following inoculation, participants will be closely observed specifically for potential allergic reactions and any AEs for the following 24 hours. Post inoculation participants will lie flat for 10 min then sit up with nose pegs on for 20 min. Participants will continue to be monitored throughout the clinical phase of the study.

#### All study interventions:

- The Investigator or designee must confirm appropriate temperature conditions have been maintained during transit for all study intervention received and any discrepancies are reported and resolved before use of the study intervention
- 2. Only participants enrolled in the study may receive study intervention and only authorised site staff may supply or administer study intervention. All study intervention must be stored in a secure, environmentally controlled, and monitored (manual or automated) area in accordance with the labelled storage conditions with access limited to the Investigator and authorised site staff
- 3. The Investigator, institution, or the head of the medical institution (where applicable) is responsible for study intervention accountability, reconciliation, and record maintenance (i.e., receipt, reconciliation, and final disposition records)
- 4. Disposal of used and unused Challenge Virus inoculum vials will be in accordance with hVIVO's SOPs
- 5. Unless specifically instructed by Sponsor, the Investigator will not destroy any partly used or unused IMP supply. On written authorisation from the Sponsor, the Investigator will send unused and partly used IMP supplies and any empty containers for destruction to the address provided at the time of authorisation. Alternatively, the destruction of unused and partly used drug supplies and any empty containers may be facilitated by the Investigator using a partner service, according to local procedures, and a destruction certificate will be provided.

#### 6.3. Randomisation and Blinding

hVIVO assigns a unique 6 digits number to each participant in the hVIVO database. This number will be used to identify a participant up to the point of randomisation, on source documents, on all study correspondence and in the study database. In Part 2 of the study, a separate randomisation number will be allocated to the participants at randomisation and will be used for allocation of study intervention (Palivizumab or Placebo).

In Part 2, a computer-generated randomisation schedule will be generated using SAS. Once assigned, that randomisation number shall not be reassigned.

Randomisation numbers will follow a 3-digit format e.g., [001]. A copy of the randomisation code list will be sent to the unblinded pharmacist preparing the study intervention, so that study intervention/placebo can be prepared for each participant as appropriate. The randomisation number encodes the participant's assignment to receive Palivizumab or Placebo in a 1:1 ratio.

Each participant will be dispensed blinded study intervention, labelled with his/her unique randomisation number, throughout the study. With the exception of the unblinded pharmacist, the unblinded statistician preparing the randomisation code list, the unblinded Clinical Research Associate (CRA) and the Quality Assurance (QA) auditors where necessary, the Investigator and all other clinical and non-clinical staff, (including the Study Statistician, data management staff), and the participants will remain blinded to the treatment allocation until after the database has been locked and approval for study unblinding has been given.

Following database lock, on receipt of authorisation from the Sponsor, a copy of the randomisation code list will be provided to the Study Statistician to conduct study unblinding prior to analysis.

Participants who are replaced as per Section 7.4 Participant Replacement Strategy will be replaced and assigned a new, unique randomisation number equaling the randomisation number of the replaced participant, plus 100. This will ensure that the replacement participant receives the same allocated, blinded treatment as the participant who is being replaced.

An individual access to a secured website will be provided to the Investigator. The website, compliant with 21CFR part 11 guidelines, will be used in the event that unblinding is required. In case of an emergency, the Investigator has the sole responsibility for determining if unblinding of a participant's intervention assignment is warranted. Participant safety must always be the first consideration in making such a determination. If the Investigator decides that unblinding is warranted, the Investigator should make every effort to contact the Sponsor prior to unblinding a participant's intervention assignment unless this could delay emergency treatment of the participant. When the investigator breaks the code, they will have to indicate on the website the reason for unblinding. The person who carried out the unblinding and the date and time of code breaking will be automatically recorded. After confirmation of the code break, the treatment allocation will appear on the screen. A notification with the treatment allocation will also be provided by email. A notification, without the treatment allocation, will be provided to the study team. Furthermore, the Sponsor must be notified within 24 hours after breaking the blind. Once the study is complete, the unblinded database will be provided to the Sponsor.

Even if the code is broken, blood samples for safety, efficacy, PK and other assessments will continue to be drawn for the remainder of the planned study period following the last dose as long as doing so will not compromise participant welfare.

The study intervention must be discontinued after unblinding, but the participant will be followed up until resolution of any AEs.

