## 7.2. Participant Discontinuation

Participants will be withdrawn from study intervention for the reasons listed below. These participants must not receive any additional intervention but should continue to be followed for safety. Additional unscheduled visits may be performed for safety reasons.

- Non-compliance with the study requirements and restrictions.
- Clinically significant abnormal laboratory findings, which in the opinion of the Investigator(s) and/or Sponsor, precludes further participation in the study.
- Development of inter-current illness which, in the opinion of the Investigator would compromise the health of the participant or the study objectives.
- The Investigator's decision that withdrawal from further participation would be in the participant's best interest.
- Termination of the study at the discretion of the Investigator(s) or Sponsor for safety, behavioural, or administrative reasons.
- The wish of the participant.

- Any intervention related SAEs.
- Anaphylactic reaction following dosing.
- The participant becomes pregnant (if pregnancy is specified as an exclusion criterion).

Participants who are withdrawn from the study, will be requested to attend an Early Withdrawal Visit, with assessments as detailed in the SoA.

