## 7.4. Participant Replacement Strategy

Participants who withdraw or are discontinued from the study may be replaced in order to achieve the planned evaluable number of participants as follows, if deemed appropriate by the PI and with the approval of the Sponsor:

- In Part 1, withdrawals or early discontinuation prior to the completion of all scheduled clinic visits up to and including Day 12 Visit may be replaced.
- In Part 2, participants who have been dosed but not inoculated may be replaced. The replacement participant will be assigned to the same group as the original (discontinued) participant.

  Participants who have been dosed and inoculated but did not complete the study may be replaced.

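### If a code-broken participant is replaced, the same-arm (number plus 100) rule tells anyone who saw the allocation the replacement's arm before enrolment

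*Protocol*

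**What the plan says.** Three rules bear on this point.

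- **Numbering (Protocol 6.3).** Anyone replaced under section 7.4 is followed by a participant who is "assigned a new, unique randomisation number equaling the randomisation number of the replaced participant, plus 100". The stated purpose is: "This will ensure that the replacement participant receives the same allocated, blinded treatment as the participant who is being replaced".
- **Replacement (Protocol 7.4, repeated in SAP 3.2.4).** A Part 2 participant who received the infusion but not the challenge may be replaced, and "The replacement participant will be assigned to the same group as the original (discontinued) participant". A second class follows: "Participants who have been dosed and inoculated but did not complete the study may be replaced". Section 7.4 gives no arm rule for this second class, but 6.3 covers every replacement made under 7.4. Replacement is discretionary: "if deemed appropriate by the PI and with the approval of the Sponsor".
- **Emergency unblinding (Protocol 6.3).** The Investigator alone decides whether to break a code. "After confirmation of the code break, the treatment allocation will appear on the screen", and a notification with the allocation also goes out by email. The study team is told that a code was broken, but not the arm. After that, "The study intervention must be discontinued after unblinding", although sampling and follow-up continue.

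**The concern.** Each rule is reasonable on its own. Same-arm replacement protects the planned 25 per arm, and on-screen disclosure is what an emergency code break is for. Together they leave a gap. A replacement is not randomised afresh but inherits an allocation, and for a code-broken participant that allocation is already known to at least one person at the site.

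What is at stake is concealment at entry and blinding afterwards, for that replacement only. Eligibility leaves the Investigator some discretion (Protocol 5.2, criterion 16). Investigators grade the directed examination signs (Protocol 8.5) that feed the URTI and LRTI definitions (SAP 4.2.1.4), and they judge AE causality (Protocol 10.3.6.5). Extended quarantine is at the PI's discretion (Protocol 8.20.1.3). That last item touches the primary endpoint indirectly, because VL-AUC runs to the end of quarantine and SAP 5.2.1.2 takes discharge as actual discharge, extensions included. SAP 3.3.2.5 does not name this situation among its examples of major deviations, so by default the replacement would enter the Evaluable set as double-blind.

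**Working it through.** **1. The target that the same-arm rule protects.** Inputs from Protocol 9.2.2: placebo mean 20.3, SD 17.8, 70% reduction, two-sided 5%, 80% power.

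- Difference = 0.70 × 20.3 = 14.21.
- n per arm = 2 × (1.960 + 0.842)² × 17.8² / 14.21² ≈ 24.6, rounded up to 25.

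This reproduces the plan's 25 per group. Normal-approximation power at 25 per arm is 0.806, against 0.800 stated. The point does not depend on these figures, and they do not change.

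**2. The chain, rule by rule.**

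- A code is broken, and the Investigator sees the arm (6.3).
- The participant is discontinued. "Anaphylactic reaction following dosing" is one listed reason in 7.2; pregnancy is another, and 10.3.11 provides for an emergency request to break the blind in that case. Table 2 lists the challenge virus among the study interventions. If discontinuation after unblinding is read to include it, a code break between Day -1 and Day 0 puts the participant in the class dosed but not challenged.
- The PI judges replacement appropriate and the Sponsor approves (7.4).
- The replacement takes the old number plus 100 and the same arm (6.3).

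No section of either document randomises such a replacement afresh, rules out replacing a code-broken participant, or passes the decision, enrolment or assessment to someone who has not seen the allocation.

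**3. What is disclosed.** Assuming the first 50 numbers are 001 to 050, replacements occupy 101 to 150. The ranges do not overlap, so a replacement's number identifies its predecessor. Under 1:1 allocation, the chance of naming the replacement's arm correctly goes from 0.5 to 1.0 for anyone who saw the predecessor's allocation. It stays at 0.5 for anyone who did not.

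**4. How many participants.** The documents give no rate of code breaks followed by replacement. As assumed values: 1/50 = 2%, 2/50 = 4%, 5/50 = 10%.

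**5. Cost of giving up arm matching for these participants only.** Information relative to an equal split = 4 × n₁ × n₂ / N², with N = 50.

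- One replacement lands in the other arm: 4 × 24 × 26 / 2500 = 0.9984.
- Two land in the same other arm: 4 × 23 × 27 / 2500 = 0.9936.

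**The case against.** The strongest reply is that this needs a code break, a discontinuation and a discretionary replacement together. Section 7.4 permits replacement but does not require it, so the site may leave the slot empty. Protocol 1.1.6.2 anticipates no dropout between dosing and inoculation. Under 7.5 (Table 5) a SUSAR halts further palivizumab administration pending review. The primary endpoint is a laboratory PCR measure, and symptom scores are self-reported by participants, who stay blinded. URTI and LRTI were added by the SAP (section 8) and are only described by group (5.4.2.4). Extended quarantine is tied to the PCR result and/or symptoms. The study is exploratory.

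All of this stands as a limit on size, but it does not close the gap. Not every code break follows a SUSAR: pregnancy is one route, a code break may reveal placebo, and dosing may restart after a SUSAR review. Table 1 lists anaphylaxis as a side effect already reported, so it may not count as unexpected; the SmPC that would settle this is not among the documents.

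A reader might infer three stronger things, which the documents do not support.

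- **That the Sponsor is equally unblinded.** The Sponsor unblinds potential SUSARs (10.3.8) and approves replacements (7.4), but nothing says that the same individuals do both. Notice of a code break to the Sponsor is not stated to include the arm.
- **That replacements are predictable even without a code break.** Sharing an arm with someone whose arm is unknown discloses nothing. Guessing from a suspected reaction remains possible, as in any blinded trial.
- **That one unblinded person does everything.** Dosing and inoculation may be done by designees or other clinical staff (6.4, 6.2.2), and the study team's notice withholds the allocation.

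**Conclusion.** The gap is real but narrow. For a participant whose code was broken and who is then discontinued and replaced, sections 6.3 and 7.4 disclose the replacement's arm, before enrolment, to whoever saw the allocation. Ordinary replacements are not affected, nor are staff who did not see it, the PCR assay itself, or the sample size and power.

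The likely extent is 2% to 4% of Part 2 if one or two cases occur, and 10% if five do. These counts are assumptions, and zero cases is quite possible. How much bias a known arm would introduce cannot be estimated from the documents. The point is worth acting on because the failure is foreseeable from the written rules and costs almost nothing to prevent. It is not a reason to doubt the trial's blinding in general.

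**What to change.** Amend Protocol 6.3 and 7.4 and SAP 3.2.4 as follows.

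- Keep the plus-100, same-arm rule for ordinary replacements.
- Where the replaced participant's code was broken, or the allocation was otherwise disclosed to anyone involved in enrolment or assessment, give the replacement the next unused number from a pre-generated, concealed 1:1 extension of the randomisation schedule, held by the unblinded pharmacist.
- Use a number range for the extension that does not collide with the plus-100 numbers. The existing notice to the study team, which reports a code break without the arm, can trigger this route.

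The cost is a few sentences and a slightly longer list. Final arm sizes may differ a little: 24/26 keeps 99.8% of the information of 25/25, and 23/27 keeps 99.4%. Dropping same-arm replacement for everyone would also work, but it gives up a deliberate means of holding 25 per arm where there is no disclosure to guard against.

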# 6.4. Study Intervention Compliance

When participants are dosed at the site, they will receive study intervention and challenge virus directly from the Investigator or designee, under medical supervision. The date and time of each dose administered in the clinic will be recorded in the source documents and recorded in the case report form (CRF). The dose of study intervention and study participant identification will be confirmed at the time of dosing by a member of the study site staff other than the person administering the study intervention.

Any non-compliance or problems with the administration of the study intervention will be recorded in the participant's source notes and reported to the Sponsor if appropriate.

